10.6.4. Efficacy

Relapse free efficacy at 4 months

 • Relapse is defined below based on a positive blood smear with or without vivax malaria symptoms.

 • A subject will be considered to have demonstrated relapse free efficacy for the purpose of the efficacy analysis if all of the following are true (also described in Figure 1): 
 • Subject is slide positive for P. vivax (per slide or source documents) at baseline. • Subject demonstrated initial clearance of P. vivax parasitemia. This is defined as a negative slide at or before the Day 29 visit. Subjects who do not meet this criteria will be censored, with time to relapse = 0 days. • Subject is not slide-positive for P. vivax at any assessment prior to or on Study Day 130 following initial parasite clearance. Subjects who are slide-positive for P. vivax will be classified as relapses, with time to relapse = (date of first positive slide) – (date of Study Day 1) days. • Subject did not take a concomitant medication with anti-malarial activity at any point between Study Day 1 and their last parasite assessment (up to and including Study Day 130). A list of all concomitant medications will be reviewed by a GSK clinician prior to unblinding the study, and classified accordingly. Subjects who did take a drug with anti-malarial activity but never had a positive asexual P. vivax parasite slide after initial clearance will be censored, with time to relapse censored at (date of last negative parasite assessment prior to concomitant medication start) – (date of Study Day 1). If a subject has not had a negative assessment prior to the concomitant medication start date, they will be censored at 0 days. • Subject is parasite-free at 4 months. This is defined as a negative asexual P. vivax parasite slide at the first parasite assessment performed on or after Study Day 110 (up to and including Study Day 130). • Subjects who do not have a positive asexual P. vivax parasite slide following initial clearance but where the final parasite assessment occurred before Study Day 110 will not have been classified by the preceding rules. These subjects will be considered to be censored, with time to relapse censored at (Date of final parasite assessment) – (date of Study Day 1). • If a subject has a relapse outcome and a censored outcome, they will be considered to be a relapse, even if the time point of the relapse is later than the time point of censoring. For example, a subject who took a medication with anti-malarial activity at Study Day 32, but remained parasite-free after initial clearance until Study Day 68 will be treated as a relapse at Study Day 68.

Figure 1 Flowchart of algorithm for relapse-free efficacy at 4 months

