3. OBJECTIVES AND ENDPOINTS

Objectives	Endpoints
Primary	

 To evaluate the pharmacokinetics (PK) of tafenoquine in children and adolescents aged ≥ 2 years to < 16 years (weighing ≥ 5 kg) with P. vivax in order to identify appropriate doses that achieve a similar exposure to that of the tafenoquine adult dose of 300 mg. 	
 AUC(0-∞) of TQ by weight band from a population PK model in pediatric subjects aged ≥ 2 years to < 16 years (weighing ≥ 5 kg).
Secondary	

 To assess the safety of tafenoquine when administered to pediatric subjects with P. vivax malaria. 	
 Description of safety data in the study population. Key safety endpoints of interest are: 
 ➤ Gastrointestinal tolerability, and ➤ Clinically relevant drops in hemoglobin. ➤ Additionally, the incidence and severity of adverse events and abnormal laboratory observations.

 To assess the clinical and parasitological efficacy of tafenoquine as a radical cure for pediatric subjects with P. vivax malaria when co-administered with chloroquine. 	
 Recurrence-free efficacy at four months post-dosing.

 To assess the PK of tafenoquine in infants aged ≥ 6 months to < 2 years (weighing ≥ 5 kg) with P. vivax (if data permit) 	
 AUC(0-∞) of TQ by weight band from a population PK model in infants aged ≥ 6 months to < 2 years (weighing ≥ 5 kg).

With regard to the secondary efficacy endpoint, it should be noted that it is not possible to determine if a subject's recurrence of malaria is a relapse (liver stage treatment failure) or a re-infection (i.e., new infection), even when using current genetic techniques. Likewise, it is not possible to determine if a recurrence is a re-infection or recrudescence (blood stage treatment failure). For the purposes of this protocol, the term 'recurrence' will be used to represent any type of malaria treatment failure. Recurrence is defined as a positive blood smear with or without vivax malaria symptoms.

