6.9.2. Prohibited Medications and Non-Drug Therapies

The following drugs are prohibited for use from 30 days prior to entry in the study through Day 120:

- Anti-malarials and other medicines with known anti-malarial activity (with the exception of CQ being given to potential subjects prior to randomization).

Results from an *in vitro* renal transporters study showed that TQ inhibits the renal transporters MATE1, MATE2-K AND OCT2. Inhibition of these transporters may explain mild, transient, asymptomatic increases of creatinine observed in previous clinical studies and may lead to increased exposure to medications excreted via these transporters. The following drugs are prohibited for a period of 21 days immediately following the blinded dose of TQ.

- Anti-diabetic drugs of the biguanide class:
 - Phenformin
 - Buformin
- Anti-arrhythmic drugs:
 - Dofetilide
 - Procainamide
 - Pilsicainide

Metformin, another biguanide anti-diabetic, may continue to be taken provided the subject has serum creatinine below the upper limit of normal and has no concomitant medical condition that increases the risk of lactic acidosis.

The use of herbal remedies during the course of the study is to be avoided. However, if taken this should be recorded in the eCRF under concomitant medication.

See [Appendix 7](#) in Section [12.7](#) for a non-exhaustive list of prohibited medicines for guidance.

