12.7. Appendix 7 – Prohibited Medications for Study Entry

Acetylsalicylic acid. (Paracetamol is the recommended antipyretic agent due to FDA requirement to record times antipyretics are given).

Antimalarials:

- 4-aminoquinolines (amodiaquine, chloroquine)
- 8 aminoquinolines (primaquine, pamaquine)
- Artemisinin derivatives
- Aryl-aminoalcohol (halofantrine, lumefantrine)
- Atovaquone
- Tetracycline e.g. doxycycline
- Quinine, Quinidine, Quinacrine, mefloquine
- Proguanil

Drugs with antimalarial activity:

This list serves to provide examples of more commonly used drugs with antimalarial activity, but is not exhaustive.

- Allopurinol
- Clindamycin
- Diamidines (e.g., Pentamidine)
- Fluroquinolones e.g. ciprofloxacin, Nalidixic acid, sparfloxacin
- Glibenclamide
- Indinavir, Saquinavir and Ritonavir
- Isoniazid
- Probenecid
- Rifampicin
- Sulfadiazine, Sulfadoxine or Sulfalene/pyrimethamine, Sulfamethoxazole/trimethoprim, Sulfasalazine (and other sulfonamides)
- Sulfacetamide

Drugs Contraindicated in G6PD deficiency:

- Melarsoprol
- Menadiol
- Methyl dopa-
- Methylthioninium chloride (i.e., Methylene Blue)
- Nalidixic acid
- Niridazole
- Nitrofurantoin

Drugs excreted via the renal transporters MATE1, MATE2-K AND OCT2:

- Phenformin
- Buformin
- Dofetilide
- Procainamide
- Pilsicainide

Others-miscellaneous:

- Phenazopyridine
- Phenylhydrazine
- Chloramphenicol

CQ interactions (source eMC):

- Amiodarone
- Antacids (Al, Ca, Mg salts) may cause reduced absorption of CQ. If required therapy must be taken well separated from CQ (at least four hours apart).
- Cimetidine inhibits metabolism of CQ (increases plasma concentration)
- Cyclosporin (CQ interaction)

In addition, refer to locally approved prescribing information.

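### Two Kaplan-Meier rules in SAP 10.6.4 need correcting: drug users are censored or kept according to what happens later, and documented failures to clear are censored at 0 days

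*SAP*

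**What the plan says.** SAP 8.1.1 plans a Kaplan-Meier point estimate and 95% confidence interval of relapse-free efficacy at four months (mITT population, dose groups combined), beside a crude n (%). SAP 10.6.4 gives the derivation.

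**Drug users.** Avoiding such drugs is part of the success definition: "Subject did not take a concomitant medication with anti-malarial activity at any point between Study Day 1 and their last parasite assessment". A child who takes one and is never slide-positive after clearance is censored at the last negative slide before the drug. If a positive slide comes later, "they will be considered to be a relapse, even if the time point of the relapse is later than the time point of censoring". The SAP's illustration is "a subject who took a medication with anti-malarial activity at Study Day 32, but remained parasite-free after initial clearance until Study Day 68", who counts as a relapse on Day 68.

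**Children who do not clear.** Clearance means a negative slide no later than the Day 29 visit. Otherwise: "Subjects who do not meet this criteria will be censored, with time to relapse = 0 days". For drug users: "If a subject has not had a negative assessment prior to the concomitant medication start date, they will be censored at 0 days". Neither sentence separates slides that stay positive from slides that are missing.

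**Related text.**
- SAP 10.12.1 says Kaplan-Meier assumes that censored children would relapse at the same rate as those still followed, and that this cannot be tested.
- Protocol section 3 says the term recurrence "will be used to represent any type of malaria treatment failure", defined by a positive smear.
- SAP 2.1 lists the change of name to relapse and the longer clearance window as departures from the protocol. It does not list removal of children who never clear.
- SAP 1.1 records that the censoring rule for children who cleared was updated to match other studies in the programme.

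**The concern.** (a) Two children with the same history up to the day the drug starts are handled differently because of what happens afterwards. The one who later relapses stays at risk and becomes an event; the one who does not is removed early. The assumption in SAP 10.12.1 then fails by construction wherever relapse after the drug is possible.

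The case can arise in practice. Protocol Appendix 7 lists drugs used for other illnesses, such as clindamycin and sulfamethoxazole/trimethoprim, and adds: "This list serves to provide examples of more commonly used drugs with antimalarial activity, but is not exhaustive".

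(b) A child censored at 0 days leaves before the first risk set, which is the same as deletion. For a child with documented positive slides, this discards an observed treatment failure. The rule that relapse overrides censoring does not help, because a relapse must follow clearance.

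The stake is the reported efficacy estimate. Protocol 9.4.2 compares it with the adult exposure-efficacy response, and SAP 7.1.1 takes efficacy into account in the dosing recommendation.

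**Working it through.** The documents give no expected four-month rate, no efficacy power, and no rates of drug use or non-clearance, so there is no plan figure to reproduce. What follows is illustration.

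**Inputs.** n=60 (Protocol 9.2). Assumed: 85% relapse-free, that is 51 of 60 with 9 failures. The adult six-month figure in Protocol 2.1.2 serves only as a scale. Standard error = √(0.85 × 0.15 / 60) = 4.6 points.

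**(a) Exact counts.** Users start the drug after the Day 8 slide and before the first relapse, so a censored user leaves before any event. The estimate is then (at risk − events) / at risk.

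| Case | SAP rule | All users censored | Drug ignored |
|---|---|---|---|
| 6 users, 1 relapses later | (55−9)/55 = 83.6% | (54−8)/54 = 85.2% | 51/60 = 85.0% |
| 12 users, 2 relapse later | (50−9)/50 = 82.0% | (48−7)/48 = 85.4% | 51/60 = 85.0% |
| 6 users, the 1 relapse suppressed | (54−8)/54 = 85.2% | (54−8)/54 = 85.2% | 52/60 = 86.7% |

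In the first row the SAP removes only the 5 users who never relapse, leaving 55 at risk with all 9 events.

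**(a) Simulation.** 20,000 trials per scenario. Relapse-free without the drug: 100/98/94/90/85% at Days 8/29/60/90/120. Drug use is independent of relapse risk. The entries are the SAP rule minus censoring all users, in points.

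| Drug effect | Start Days 9–115: 5/10/20% users | Start Days 9–28: 5/10/20% users |
|---|---|---|
| None | −0.5/−1.0/−2.1 | −0.7/−1.4/−3.1 |
| Relapse hazard halved | −0.3/−0.5/−1.1 | −0.3/−0.7/−1.6 |
| Full suppression | 0 | 0 |

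Censoring all users gives 84.9–85.1% in all 18 scenarios. Ignoring the drug is 0.5 to 3.0 points too high under full suppression.

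**(b) Exact counts.** Of the 9 failures, c are documented non-clearers. The SAP estimate is 51/(60−c); counting them as failures gives 51/60 = 85.0%.
- c=1: 51/59 = 86.4% (+1.4)
- c=2: 51/58 = 87.9% (+2.9)
- c=3: 51/57 = 89.5% (+4.5)

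That is 1.4 to 1.5 points per child.

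**Both together**, with 6 users of whom 1 relapses:
- Plus 1 non-clearer: SAP (54−8)/54 = 85.2%; corrected (54−8)/54 = 85.2%. The errors cancel.
- Plus 2 non-clearers: SAP (53−7)/53 = 86.8%; corrected 46/54 = 85.2%.

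**The case against.** - **Alignment and direction.** The censoring rule was aligned with other studies on purpose, and rule (a) errs against the drug. Both are true. Neither makes outcome-dependent censoring valid, and because (b) works the other way the overall estimate cannot be called conservative.
- **Censoring all users is not neutral.** This stands. In a simulation with 10% users, start Days 9–115 and no drug effect, users were given twice the relapse hazard: truth 83.7%, SAP rule 82.8%, all users censored 84.6%. At three times the hazard: 82.6%, 81.7% and 84.1%. The excess risk is an assumption. Censoring all users is unbiased only if drug use is unrelated to relapse risk, so ignoring drug use must be reported beside it.
- **Protocol section 3 does not name non-clearance.** This stands. A reader might infer an explicit protocol rule that non-clearers are failures; the text supports this only through its wording on any type of treatment failure.
- **Non-clearers remain visible.** They fail the crude definition and appear in the listings. But the two summaries then disagree: with 9 later relapses plus 3 non-clearers, crude is 48/60 = 80.0% and Kaplan-Meier is 48/57 = 84.2%.
- **Few children may be affected.** Protocol 6.9.2 says of antimalarials and drugs with such activity: "The following drugs are prohibited for use from 30 days prior to entry in the study through Day 120". With no users and no non-clearers the effect is zero. Efficacy is secondary, unpowered and without hypotheses.
- **Figure 1** of the algorithm is not visible in the text available, so only the written rules were checked.

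**Conclusion.** Both rules are wrong as written. Rule (a) makes censoring depend on the later outcome and lowers the estimate unless the drug fully suppresses relapse. Rule (b) deletes documented failures and raises it by about 1.4 points per child at n=60. With 5–10% users (0 to 1.4 points) or one non-clearer, each effect is well below the standard error of about 4.6 points. All sizes rest on assumed rates. Confidence is medium.

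Three stronger readings are not supported:
- That the plan inflates efficacy. The two biases have opposite signs, can cancel, and have no documented rates.
- That rescue treatment after a relapse is mishandled. A positive slide after clearance and before the drug is already an event at its own date.
- That all censoring at 0 days is wrong. It is reasonable for a child with no usable post-baseline slide.

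The primary pharmacokinetic analysis is not affected.

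**What to change.** Revise SAP 10.6.4, applying the rules in this order.

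1. **Classify documented failures to clear first, for all children.** A child still slide-positive at the Day 29 visit with no earlier post-dose negative slide is an event at that slide. A child who takes an antimalarial after a positive slide from the Day 8 window onward, and before any negative slide, is an event at the last positive slide before the drug, whatever later slides show. Keep censoring at 0 days for children with no usable post-baseline slide. For children positive at Day 8 and then lost, keep it in the main analysis and count them as failures in a sensitivity analysis.
2. **Then treat all remaining users whose drug start precedes any relapse alike.** Censor each at the last negative slide before the drug, and delete the override for relapses after the drug. Report beside it the analysis that ignores drug use for all children. State that the first is unbiased only if drug use is unrelated to relapse risk (too high if users are at higher risk), and the second only if the drug does not affect relapse.
3. **Keep the current rule as a sensitivity analysis** for comparison with the adult studies.

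The order matters. Take a child positive at Day 8, treated, negative at Day 29 and positive at Day 90, who is now an event. Deleting the override alone would censor that child at 0 days and move 51/60 = 85.0% to 51/59 = 86.4%. Under step 1 the child is an event at the Day 8 slide.

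The cost is SAP wording and derivation code, with no new data. The headline rate may move slightly, the programme-aligned rule becomes secondary, and the standard error rises to about 4.7 to 5.2 points with 5–20% users.

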10.6.5. Pharmacokinetic

See [Appendix 13](#).

10.7. Appendix 7: Premature Withdrawals & Handling of Missing Data

10.7.1. Premature Withdrawals

Element	Reporting Detail
General	
 • Subject study completion (i.e. as specified in the protocol) is defined as a subject who attends all treatment and follow-up visits. • Withdrawn subjects will not be replaced in the study. • All available data from subjects who were withdrawn from the study will be listed and all available planned data will be included in summary tables and figures, unless otherwise specified.

10.7.2. Handling of Missing Data

Element	Reporting Detail
General	
 • Missing data occurs when any requested data is not provided, leading to blank fields on the collection instrument : 
 ○ These data will be indicated by the use of a “blank” in subject listing displays. Unless all data for a specific visit are missing in which case the data is excluded from the table. ○ Answers such as “Not applicable” and “Not evaluable” are not considered to be missing data and should be displayed as such.
Outliers	
 • Any subjects excluded from the summaries and/or statistical analyses due to outlying data will be documented along with the reason for exclusion in the clinical study report.

10.7.2.1. Handling of Missing Dates

Element	Reporting Detail
Adverse Events	
 • It is not possible to record partial dates in the eCRF for AEs. • Completely missing start or end dates will remain missing, with no imputation applied. Consequently, time to onset and duration of such events will be missing. • AEs with entirely missing or unknown start dates will be assumed to be treatment emergent for reporting. • AEs with missing end dates are not anticipated to affect reporting.
Concomitant medications	
 • Where the start or stop date of a concomitant medication record is entirely missing or unknown, the eCRF flags 'Taken prior to study?' and 'Ongoing medication?' will be used in order to derive whether it is prior or concurrent. • If these flags are also missing, then it will be assumed that it is concurrent. • In the event that use of the same medication is recorded at more than one visit (and if this has not been collapsed to one record), the eCRF flags will be cross-checked for both records.

10.7.2.2. Handling of Partial Dates

Element	Reporting Detail
General	Partial dates will be displayed as captured in subject listing displays.
Concomitant Medications	
● Partial dates for any concomitant medications recorded in the CRF will be imputed using the following convention:
○ If the partial date is a start date, a '01' will be used for the day and 'Jan' will be used for the month○ If the partial date is a stop date, a '28/29/30/31' will be used for the day (dependent on the month and year) and 'Dec' will be used for the month.● The recorded partial date will be displayed in listings.
Adverse Events	
● It is not possible to record partial dates in the eCRF for AEs.

10.8. Appendix 8: Values of Potential Clinical Importance

10.8.1. Laboratory Values

Element	Reporting Detail
F1 flag	
 Denotes a value that falls outside the normal range. Used by the laboratory and provided directly by the site for inclusion on the database.
F2 flag	
 Denotes a value that has increased or decreased from baseline by more than a specified amount. Defined below
F3 flag	
 Denotes a value that falls outside an extended normal range. This range is independent of any change from baseline or other values. F3 range is calculated as: 
 Absolute: pre-specified limits. Proportional: upper and lower limits are defined by multiplying the normal range limits by different factors Defined below
General	
 If a subject has both 'high' and 'low' values flagged for a parameter during the study, they will be reported once under each category.

Hematology				
Laboratory Parameter	Units	Category	Clinical Concern Range	
			Low Flag (< x)	High Flag (>x)
Hemoglobin	G/L	F2	Max(baseline – >30 g/L, ≥30% decline from baseline)	
Platelet count	10 ⁹ /L	F3	50	
Lymphocytes	10 ⁹ /L	F3	0.5	4
Eosinophils	10 ⁹ /L	F3		1.5
Reticulocytes count	10 ¹² /L	F3		1xULN

Clinical Chemistry				
Laboratory Parameter	Units	Category	Clinical Concern Range	
			Low Flag (< x)	High Flag (>x)
Creatine kinase (CPK) ^a	IU/L	F3		5x ULN
Creatinine ^a	μmol/L	F2		3x baseline
		F3		3x ULN

Clinical Chemistry				
Laboratory Parameter	Units	Category	Clinical Concern Range	
			Low Flag (< x)	High Flag (>x)
Urea (BUN) ^b	mmol/L	F3		11.067
Alanine aminotransferase	IU/L	F3		3x ULN
Aspartate aminotransferase	IU/L	F3		3x ULN
Total bilirubin	μmol/L	F3		1.5x ULN
Indirect bilirubin	μmol/L	F3		1.5x ULN
Alkaline phosphatase	IU/L	F3		2.5xULN

a. CTC AE criteria

b. FDA industry toxicity grading scale for healthy volunteer adults and adolescents in preventative vaccine trials

10.9. Appendix 9: Multicenter Studies**10.9.1. Methods for Handling Centres**

- In this multicentre global study, enrolment will be presented by investigator site and country.

10.10. Appendix 10: Examination of Covariates, Subgroups & Other Strata

10.10.1. Handling of Covariates, Subgroups & Other Strata

- Summaries will be presented by dose group, if the percentage of subjects within a particular dose group is small then the groups may be refined prior to final reporting.

10.10.1.1. Footnote Regarding Dose Groups

- For all data displays presented by dose group, the following footnote should be added:

Weight bands were: TQ 50mg = ≥ 5 - ≤ 10 kg; TQ 100mg = > 10 - ≤ 20 kg (Cohort 2 and 3); TQ 150mg = > 10 - ≤ 20 kg (Cohort 1); TQ 200mg = > 20 kg- ≤ 35 kg; TQ 300mg = > 35 kg

10.11. Appendix 11: Multiple Comparisons & Multiplicity**10.11.1. Handling of Multiple Comparisons & Multiplicity**

No hypothesis testing will be performed in this study, all analyses are exploratory and so no adjustments for multiplicity are required.

10.12. Appendix 12: Model Checking and Diagnostics for Statistical Analyses

10.12.1. Statistical Analysis Assumptions

No statistical modelling is being performed. Kaplan-Meier curves are being fitted which assume that censored subjects have the same prospect of relapse as those being followed, however, it is not possible to test this assumption. All other data is being summarised only.

10.13. Appendix 13: Population Pharmacokinetic Analyses

10.13.1. Introduction

The purpose of the data analyses outlined in this document is to characterise the systemic exposure of Tafenoquine (TQ) administered as a single dose to pediatric subjects with *P. vivax* malaria with a model based population pharmacokinetic (POP PK) approach. The influence of subject demographics, baseline characteristics and any other relevant covariate on the PK of TQ in pediatric subjects with malaria will be investigated to identify a dose regimen that provides systemic TQ exposure across various weight bands in pediatric subjects similar to that in adult population.

Given the small subject numbers in this study, and the sparse nature of PK sampling, a model-based population PK analysis using non-linear mixed effects is a robust approach for assessing the PK of TQ in the pediatric population.

